5. STUDY TREATMENTS

5.1 Treatment Arms

5.1.1 Description

Regardless of which trial arm participants are allocated to, they will continue to receive all other non-rectal aspects of a ‘bowel routine’ that constitutes ‘standard care’. This includes dietary and fluid management, the use of timed toileting (eliminating at the same time each day), pr checks prior to commencing and at the end of bowel care and the use of aperients titrated by stool consistency documented using the Bristol stool chart.

Intervention Group

The participant will use transanal irrigation daily or second daily (depending upon his/her current bowel routine) for a period of 6 weeks. Bowel care will be provided by the participant or carers trained in use of the irrigation system. Bowel care will occur at the usual time that s/he attends to his/her toileting and all participants will use the system whilst seated on a commode chair over their toilet.

Control Group

The participant will continue to use rectal medication / procedures as usual for a period of six weeks. Bowel care will be provided by the participant or carers. Bowel care will occur at the usual time that s/he attends to his/her toileting and all participants will have bowel care whilst seated on a commode chair over their toilet.

5.1.2 Dosage and Route of Administration

Intervention Group

All participants will commence on 400mL of luke-warm water (as per the manufacturer’s instructions) delivered via the rectum. Water volume will be titrated up to a maximum of 1 L (as per the manufacturer’s instructions).

Control Group

All participants will continue with their usual dosage of micro enemas or suppositories. This is typically 5mL of Sodium citrate dihydrate, sodium lauryl sulfoacetate and sorbitol micro enema

(Microlax®) or 1-2 glycerol suppositories. Micro enemas and suppositories are administered via the rectum.

6 PARTICIPANT ENROLMENT AND RANDOMISATION

6.1 Recruitment

Recruitment will occur from the spinal outpatient department at Royal North Shore Hospital and directly from the community. Participants will be pre-screened by their Primary Nurses / Treating Clinicians. If a potential participant is deemed appropriate for the trial, the participant will be asked to provide verbal consent for his/her contact details (name and phone number) to be shared with the Site Principal Investigator. The Site Principal Investigator will then contact the potential participant within 2 weeks to further explain the trial and ensure the participant is eligible. If the participant is eligible and interested in being involved, he/she will be provided with a Participant Information Sheet. A log will be kept of all people referred to the trial regardless of whether a potential participant is eligible and/or agrees to participate.

6.2 Eligibility Criteria

6.2.1 Inclusion Criteria

People will be eligible for inclusion if they:

- sustained a spinal cord injury more than 6 months prior or have Spina Bifida
- have a Neurogenic Bowel Dysfunction Score (3) ≥ 3
- are aged 18 years or over at the time of consent
- are willing to participate in the trial
- have been recommended to trial transanal irrigation by a clinician because they spend more than 30 mins on toileting AND ANY OF THE FOLLOWING:
 - had more than 1 episode of faecal incontinence per month
 - had a Bristol stool chart result of <3 or >6 for more than 3 cycles of bowel care
 - experienced abdominal symptoms such as bloating/cramping
 - experienced inconsistency with defaecation
 - experienced rectal symptoms (bleeding haemorrhoids, rectal prolapse, fissures etc)
 - experienced autonomic dysreflexia in response to bowel care

6.2.2 Exclusion Criteria

People will be excluded if:

- they are unable to co-operate (e.g. a serious medical condition, cognitive impairment, drug dependency, psychiatric illness, and behavioural problem)
- they are unable to speak sufficient English to provide informed consent
- they are currently using bisacodyl suppositories or enemas as the primary method for managing bowel care routine.
- transanal irrigation is contraindicated for use (36) for any of the following reasons:
 - anal / rectal stenosis
 - active inflammatory bowel disease
 - acute diverticulitis
 - colorectal cancer

- within 3 months of rectal surgery
- within 4 weeks of endoscopic polypectomy
- ischaemic colitis
- current or planned pregnancy
- long term steroid therapy
- radiotherapy to the pelvis
- dense sigmoid disease
- on anticoagulants (warfarin, apixaban, rivaroxaban, dabigatran)

6.3 Informed Consent Process

Potential participants will be given a copy of the Participant Information Sheet to review, and will be informed both verbally, and in writing (via the Participant Information Sheet) that their participation in the trial is entirely voluntary and it will not affect their current or future relationships with the treating clinicians or the Principal Investigators. Participants will be encouraged to ask questions regarding the trial or discuss with family and friends before consent is given. Once the essential trial information has been provided, the participants will be asked to give informed consent to participate in the trial by signing the Consent Form in the presence of a witness. These forms will be dated and retained by the Investigator at the site where all research data will be kept, and a copy will be provided to the participant. Any ongoing dependent relationship between clinicians and the participant will not be affected if a participant chooses to withdraw after consent has been given. It is most unlikely that the Principal Investigators and participants will be in any ongoing dependent relationship.

6.4 Enrolment and Randomisation Procedures

Participants will be enrolled into the study after the informed consent process has been completed. Because half of the participants will be randomised into the control group, procurement and training of the preferred TAI system will occur *prior* to randomisation for each participant so that the control arm will be able to commence TAI as soon as they complete the study if they wish to. The investigator responsible for collecting the baseline data will check that each participant meets the inclusion criteria. They will collect and confirm all demographic information including date of birth, sex, details about the injury/condition, including date of injury as well as a SCI bowel function data set. Baseline data on the primary and 4 of the 6 secondary outcome measures will be also be collected prior to randomisation.

A secure random-allocation schedule will be computer-generated prior to commencement of the trial by an independent person and kept at a central off-site location. The randomisation schedule will be blocked (1:1) to ensure equal numbers of participants are randomised to the treatment and control arms. A participant will be entered into the trial when baseline details are logged, and the allocation is provided. At this point, the participant will receive a study number, and this will be documented on all study documents.

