Selection Criteria	
People will be eligible for inclusion if they:
 
 • have sustained a spinal cord injury more than 6 months prior or have Spina Bifida • have a Neurogenic Bowel Dysfunction Score (3) ≥ 3 • are aged 18 years or over at the time of consent • are willing to participate in the trial • have been recommended to trial transanal irrigation by a clinician because they spend more than 30 minutes on toileting AND ANY ONE OF THE FOLLOWING: 
 ○ had more than 1 episode of faecal incontinence per month ○ had a Bristol stool chart result of <3 or >6 for more than 3 cycles of bowel care ○ experienced abdominal symptoms such as bloating/cramping ○ experienced inconsistency with defaecation ○ experienced rectal symptoms (bleeding haemorrhoids, rectal prolapse, fissures etc) ○ experienced autonomic dysreflexia in response to bowel care
Study Procedures	
All eligible people living in the community will be invited to participate. If agreeable they will have baseline data collected and then be randomised into treatment group (transanal irrigation) or control group (standard bowel care) for six weeks. Transanal irrigation involves administration of approximately 400mL of luke-warm water via the rectum using a commercialised 'kit'. This kit includes a rectal catheter, tubing and a reservoir to hold the water. The principle is to 'flush' the lower colon clear of stool to avoid constipation and incontinence. Standard bowel care involves the use of micro enemas/suppositories, digital stimulation of the rectal sphincter, manual evacuation of stool or a combination of enemas/suppositories and digital stimulation. Outcomes will be assessed at 6 weeks post intervention by blinded assessors.

Statistical Procedures	24 participants will be required to detect a between group difference of 20 minutes on the primary outcome. This assumes

	an α level of 0.5%, a SD of 18 minutes and a correlation between pre and post values of 0.4. Regression models will be used to determine between group differences (and 95% CI). Results will be interpreted with respect to the minimally worthwhile treatment effect.
Duration of the study	The trial is expected to take approximately 2 years to complete. We anticipate the recruitment will commence in March 2021.

GLOSSARY OF ABBREVIATIONS

ABBREVIATION	TERM
ANZCTR	The Australian and New Zealand Clinical Trials Registry

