4.3 Study sites

The study is community based; therefore, participants will be recruited from either the spinal outpatient departments of Royal North Shore Hospital and Prince of Wales Hospital or via the community.

All study nurses will receive education and training on the set up and use of the 3 main transanal irrigation systems and this will be supported with a procedural document to ensure consistency.

It is anticipated that 12 participants will be recruited from New South Wales and 12 participants from Queensland.

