11 STATISTICAL METHODS

11.1 Sample Size Estimation

The minimum worthwhile treatment effect for this trial has been defined as 20 minutes. This is based on preliminary retrospective data (n=15) collected by the principal investigator after taking into account the time bowel care typically takes (i.e., 41 minutes). Therefore, a sample of 24 participants is required for an 80% power to demonstrate statistical significance on the primary outcome (time to complete bowel care) with an α level of 0.05 and with a worst-case dropout rate of 5%. This assumes a standard deviation (SD) of 18 minutes and a correlation of 0.04 to pre-post (before adjustment for the within-subject design). The estimated SD was derived from preliminary data collected as above (non-published data) and from the post data reported in the trial conducted by Christensen et al (27).

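### A single 1:1 blocked schedule with no named stratification factor leaves balance across the two recruiting states to chance; separate lists by state would secure it at little cost

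*Protocol*

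**What the plan says.** Under Section 6.4, an independent person produces one computer-generated schedule before the trial begins and holds it centrally, away from the sites. The blocking has one stated purpose: "The randomisation schedule will be blocked (1:1) to ensure equal numbers of participants are randomised to the treatment and control arms". Neither a stratification factor nor a block size is given.

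Section 4.3 sets out the expected geography: "It is anticipated that 12 participants will be recruited from New South Wales and 12 participants from Queensland". It also names two hospital outpatient departments alongside community recruitment. Section 6.1 names only one: "Recruitment will occur from the spinal outpatient department at Royal North Shore Hospital and directly from the community". Neither section assigns a recruitment source to a state.

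On staff, Section 4.3 gives all study nurses the same training, backed by a procedural document. Section 8 has one blinded assessor collecting a participant's data at both baseline and week 6.

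The target is in Section 11.1: "The minimum worthwhile treatment effect for this trial has been defined as 20 minutes", and "a sample of 24 participants is required for an 80% power". Section 11.3 specifies regression without listing covariates. That detail is commonly left to a statistical analysis plan and is not criticised here.

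**The concern.** State is a two-level factor of planned equal size that is known before randomisation, and the schedule as described does nothing to balance it. The outcome is a timed procedure carried out by the participant or a carer. Local staff, assessors and recruitment sources may differ by state, although the protocol does not say that they do. If bowel-care times differ between states for any reason, an uneven split across arms of 12 carries part of that difference into the treatment estimate.

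An analysis plan could add a state term later, but it could not restore balance once the list has been used. Section 2.3 gives a more precise estimate as a reason for running the trial, so avoidable imprecision matters here.

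**Working it through.** **Sample size, to fix the working assumptions.** Per arm, n = 2 × (1.960 + 0.842)² × SD² × (1 − r²) / δ², with SD 18, δ 20, two-sided α 0.05 (sidedness assumed) and 80% power.
- Synopsis correlation ("a SD of 18 minutes and a correlation between pre and post values of 0.4"): 2 × 7.849 × 272.16 / 400 = 10.7, so 11. Then 11 / 0.95 = 11.6, so 12 per arm and 24 in total. This reproduces the plan's figure.
- Section 11.1 correlation ("This assumes a standard deviation (SD) of 18 minutes and a correlation of 0.04 to pre-post"): 13 per arm, 14 after 5% dropout, 28 in total. This does not reproduce it.

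The conflict between 0.4 and 0.04 is a separate matter. I use 0.4 below because it gives the plan's 24.

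**Chance of imbalance.** Let X be the number of New South Wales participants allocated to TAI, with 12 per state, 12 per arm and state independent of list position. Then P(X = k) = C(12,k)² / C(24,12), where C(24,12) = 2,704,156.
- 6:6: 924² / 2,704,156 = 0.316
- 7:5, either way: 2 × 0.2320 = 0.464
- 8:4, either way: 2 × 0.0906 = 0.181
- 9:3, either way: 2 × 0.0179 = 0.036
- 10:2 or worse: 0.003

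So 8:4 or worse has probability 0.220, and 9:3 or worse 0.039. Simulation with block sizes from 2 to 24 gives 0.21 to 0.22 for 8:4 or worse, so blocking the single list gives no real protection.

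**Shift in the estimate.** At 8:4 the arms differ in state share by 8/12 − 4/12 = 1/3; at 9:3, by 1/2. The between-state difference D is not in the protocol, so a range is assumed.

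| D (min) | 8:4, unadjusted | 9:3, unadjusted | 8:4 after baseline adjustment |
|---|---|---|---|
| 5 | 1.7 | 2.5 | about 1.0 |
| 10 | 3.3 | 5.0 | about 2.0 |
| 15 | 5.0 | 7.5 | about 3.0 |

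The last column assumes that D is the same at baseline and week 6 and that the baseline slope is 0.4, so 60% of the shift remains. The fitted slope would be somewhat steeper, because state itself adds to the pre-post correlation, so these are upper values. With a slope of 0.04, 96% would remain.

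**Precision and power.** The residual SD is 18 × √(1 − 0.16) = 16.5, so the error variance of the arm difference is 272.16 × 2/12 = 45.36. The state-share difference has variance 1/23 over randomisations. With state ignored, SE = √(45.36 + D²/23). Power is from 6,000 simulated trials per setting, with a 20-minute effect and no dropout. D here is the difference left after baseline adjustment.

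| D (min) | SE, one list, state ignored | Power, one list, state ignored | Power, one list, state in model | Power, two lists, state in model |
|---|---|---|---|---|
| 0 | 6.7 | 81% | 79% | 81% |
| 5 | 6.8 | 80% | 79% | 81% |
| 10 | 7.1 | 78% | 79% | 81% |
| 15 | 7.4 | 73% | 79% | 81% |

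In every setting the mean estimate stays at the true effect. Type I error with one list and state ignored is about 5%. Stratifying but leaving state out of the model is conservative: at D = 15, type I error is about 3% and power about 75%.

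**The case against.** One central blocked list is a defensible choice for 24 participants. The protocol is silent on stratification; it does not rule it out. The chance of a 7:5 split or better is 78%. Over randomisations there is no bias, and the confidence interval already reflects this source of variation. The minutes depend on an assumed D, and baseline adjustment, which the assumed pre-post correlation implies, removes part of the shift. A state term alone brings power to about 79%, so stratification adds only about two points. Separate short lists are also easier to predict when participants and study nurses are unblinded (Section 6.5).

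All of this stands, and it limits the size of the point. It does not remove it, because balance can be secured only before the list is generated.

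A reader might infer that nurses, assessors and referral routes do differ by state, or that Queensland participants come only from the community. The documents do not support either. Nurse training is common, the assessor is the same at both time points, and recruitment sources are not tied to states. A reader might also infer that the treatment effect is confounded with state. Random allocation does not permit that reading; what remains is imbalance in a given realisation.

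**Conclusion.** The point holds as a modest, inexpensive design improvement. It is not a contradiction or an error in the protocol. As described, the schedule leaves a 22% chance of an 8:4 or worse split by state and a 4% chance of 9:3 or worse, if the anticipated 12 and 12 are recruited. The consequence depends on a between-state difference that the protocol does not give. Over an illustrative 5 to 15 minutes, an 8:4 split moves the unadjusted estimate by 8% to 25% of the 20-minute worthwhile effect (1.7/20 to 5.0/20), and by less after baseline adjustment. Ignoring state would cost about 3 points of power at 10 minutes and 8 at 15, taking the whole difference to survive baseline adjustment. If the states do not differ, nothing is lost.

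**What to change.** In Section 6.4, before the schedule is generated, specify two 1:1 blocked lists, one for New South Wales and one for Queensland. Block sizes should vary and be known only to the independent list holder. Include state as a fixed term in the primary regression. The two changes belong together, since stratifying without the model term makes the test conservative. If the investigators prefer a single list, Section 6.4 should say so and give the reason.

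The costs are a second list and one degree of freedom. If recruitment stops within a block, the arms may differ overall by one or two. Allocation is somewhat more predictable within a state, which varying block sizes limit. The sample size stays at 24. If 12 are recruited in each state and the blocks close at 12, each arm has six from each state.

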6.5 Blinding Arrangements

It is not possible to blind the participants, study nurses or carers to allocation. However, all assessors will be blinded. Additionally, all Associate Investigators will remain blinded. To ensure this, the study nurses, participant and / or carers delivering the bowel care will be asked not to discuss any aspects of their bowel care with the associate investigator(s). The success of blinding for the assessor/s will be checked following the 6-week assessment.

6.6 Breaking of the Study Blind

6.6.1 On Study

Blinding will be broken if deemed necessary for safety. In addition, after the blinded assessor collects all assessments at six weeks, s/he will ask participants some open-ended questions that will invariably unblind the assessor.

6.6.2 Following Completion of the Study

Blinding will only be broken upon completion of locking of the database and completion of the statistical analysis.

6.7 Participant Withdrawal

6.7.1 Reasons for withdrawal

The following categories of withdrawal are possible for each participant:

Withdrawal from the trial and lost to follow-up – participant decides to withdraw from the trial and any further assessments.

Withdrawal from the trial – participant decides to withdraw from the trial but agrees to further assessments.

Lost to follow up – participant does not notify trial staff the s/he wishes to withdraw from the trial and cannot be contacted, therefore follow up assessments do not occur.

The consent form will advise participants that all data will be used if they are lost to follow up or choose to withdraw from the trial. However, there will be an option in the withdrawal of consent form to revoke consent for the use of data already collected.

The date and reason for any type of withdrawal will be recorded in the participant source file and on the completion page of the CRF. Where a participant exercises his/her right to discontinue participation in the trial, s/he will still be invited to participate in the follow-up assessment. Missing data will not be imputed. If >5% of data are missing, a sensitivity analysis will be done to determine the effect of the missing at random assumption.

6.7.2 Replacements

Withdrawals or losses after randomisation will not be replaced.

6.8 Trial Closure

The trial will not be stopped for futility but will be stopped if there are reasons for concern about safety. All Adverse and Serious Adverse Events will be reviewed by a safety monitoring board with an independent medical monitor, [name] who will be consulted if there are any reasons for concern. There will be no follow-up of participants after their 6-week assessment.

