4.2 Study Design

The trial will be a community based, randomised controlled trial. All eligible participants will be invited to participate. Participants will be randomised to either transanal irrigation (TAI) (intervention) or standard care (control).

Participants allocated into the intervention group will commence transanal irrigation including training and support from a Registered Nurse with experience in the procedure. All aspects of transanal irrigation will be individualised to the participant as is current practice when establishing a routine with TAI. Participants allocated into the control group will continue with their current bowel care routines.

The primary outcome will be time to complete routine bowel care at six weeks.

Participants will not be blinded to their group allocation because of the nature of the system and the need for participant / carer training, however, the assessor will be blinded to group allocation.

All participants will continue to receive all non-rectal interventions that constitute 'usual or standard care'. This includes the use of oral aperients, adequate fluid intake, and appropriate dietary intake, timing of bowel care and pr checks and digital stimulation as required (31).

All design features important for minimising bias will be adhered to and the trial will be registered with The Australian and New Zealand Clinical Trials Registry (ANZCTR). The minimally worthwhile treatment effect and statistical analyses will be set prior to the commencement of the trial in accordance with best practice. All relevant details enabling the compilation of a CONSORT flow diagram will be recorded and reported.

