6.9 Continuation of Therapy

All participants in the intervention group will be free to continue with the therapy if they are happy with the product and procedure. Participants in the control group will be free to pursue TAI with their treating clinicians but this will not be supported or supervised by the trial.

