7 STUDY VISITS AND PROCEDURES SCHEDULE

Procedure Schedule	Screening and recruitment	Assessment at baseline		Intervention	Assessment at 6- weeks post randomisation	
	-6 to -1 week	-7 to 0 days		Week 1 - 6	Week 7	
Protocol Activity:		1st visit	2nd visit		1st visit	2nd visit
Informed Consent	✓					
Eligibility Checklist	✓					
Demographic details	✓					
Procure TAI Device	✓					
Training on how to use TAI	✓					
Randomisation			✓			
Adverse Events Check		✓	✓	✓✓✓✓✓✓	✓	✓
Outcome measures:						
Neurogenic Bowel Dysfunction Score		✓	✓		✓	✓
Time to complete bowel care (assessor)		✓	✓		✓	✓
Time to complete bowel care (participant)		✓	✓	✓✓		
CCCSS		✓	✓		✓	✓
St Mark's Scale		✓	✓		✓	✓
SCI-QOL, BMD		✓	✓		✓	✓
Global Impression of Change					✓	✓
Blinding question Assessor		✓	✓		✓	✓
End of Study checklist						✓

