10 SERIOUS ADVERSE EVENT REPORTING

10.1 Definitions

10.1.1 Serious Adverse Event (SAE) / Serious Adverse Reaction (SAR)

A Serious Adverse Event (SAE) is any unforeseen medical event that occurs during clinical research that:

- results in participant death
- is life-threatening to the participant
- requires the inpatient hospitalisation or prolongation of existing hospitalisation for the participant leads to the participant having a persistent or significant disability/incapacity.
- leads to a congenital anomaly or birth defects.

In the context of a SAE/SAR definition, the term life-threatening refers to an event in which the participant was at risk of death at the time of the event, not an event that hypothetically might have caused death if it were more severe. Medical and scientific judgement should be exercised in deciding whether an adverse event/reaction should be classified as serious. Important medical events that are not immediately life-threatening or do not result in death or hospitalisation but may jeopardise the participant or may require intervention to prevent one of the other outcomes listed in the definition above will also be considered serious (37).

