10.2 Eliciting Serious Adverse Event Information

All participants and trial nursing staff will be provided with written definitions for SAE/SADE, SUSAR, USADE and SSI with trial office phone number for making contact in the event that this occurs during the trial. The details will be outlined on the Assessment and Documentation of Serious Adverse Events Form.

All SAEs will be evaluated by seriousness, causality and expectedness (38). All EOs will be identified on the Serious Adverse Event/Reaction case report form (CRF) to differentiate between known, unexpected SAE/SARs, SUSARS, and ASADE/USADEs. Additionally, the Investigators will conduct safety monitoring and reporting requirements for this study in accordance with the NSW Health policy directive PD2017_039 inclusive of any SSIs (38).

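### The no-follow-up rule in Section 6.8 makes no exception for adverse events still open at the last visit, so their outcome cannot be recorded

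*Protocol*

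**What the plan says.** **End of collection.** Protocol Section 6.8 (Trial Closure) says "There will be no follow-up of participants after their 6-week assessment". In the Section 7 schedule, the row "Adverse Events Check" is ticked at both baseline visits, six times in Weeks 1–6, and at both Week 7 visits. The second Week 7 visit is the last column. Section 6.9 lets intervention participants carry on with TAI afterwards. Controls may take it up with their own clinicians, but "this will not be supported or supervised by the trial".

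**What is asked of the safety data.** Sections 9.2 and 10.2 require every AE and SAE to be evaluated on seriousness, causality and whether it was expected. Section 6.8 sends all of them to a safety board. The seriousness criteria in Section 10.1.1 include an event that "leads to the participant having a persistent or significant disability/incapacity". For serious events outside visits, Section 10.2 supplies written definitions "with trial office phone number for making contact in the event that this occurs during the trial".

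**Start of collection.** The Section 7 row "Training on how to use TAI" is ticked only under screening (-6 to -1 week), where there is no adverse-event tick. Section 6.4 agrees that "procurement and training of the preferred TAI system will occur" before randomisation, for every participant. Section 4.2 (Study Design) reads differently: "Participants allocated into the intervention group will commence transanal irrigation including training and support from a Registered Nurse".

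**The concern.** A rule that ends outcome assessment at six weeks is a normal design choice. The sentence in 6.8 goes further. It ends all follow-up of participants, and neither Sections 9 and 10 nor any other part of the protocol carves out events that are unresolved at the last contact.

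For such an event, the case report form would hold an onset, a grading made on that day, and no outcome. If it later led to hospital admission or left lasting disability, the trial would have no planned way to find out. The safety board would be reviewing an unfinished record. With only 12 participants on TAI, each device-related event is a large part of the trial's safety information, so a missing outcome matters more than it would in a large trial.

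A smaller gap lies at the other end. The device is procured and training given before the first scheduled adverse-event check, and the protocol does not say when adverse-event reporting opens or how far back the first check should ask.

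**Working it through.** **1. Does the stated timeline contain any later contact?** Section 4.4 puts final data collection in mid April 2023 if recruitment runs to 1 March 2023. Taking 1 March as the last randomisation:
- 1 March + 42 days = 12 April (end of week 6)
- days 43 to 49 (Week 7) = 13 to 19 April

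This reproduces mid April, so the timeline ends at the Week 7 visits. Planned safety follow-up after the second Week 7 visit is 0 days.

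**2. The provisions set side by side.**

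| Provision | Place | Effect on an event open at the last visit |
|---|---|---|
| Last adverse-event check | Section 7, second Week 7 visit | It is recorded |
| No follow-up afterwards | Section 6.8 | No further contact |
| Telephone number for serious events | Section 10.2 | Covers serious events arising during the trial; sets no duty to trace an outcome |
| Evaluation of every event | Sections 9.2, 10.2 | Done on what is known that day |
| Exception for open events | none found | – |

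**3. Illustration of size.** The protocol gives no event rate or duration. Assume that onset is uniform over the 49 days from randomisation to the end of Week 7, and that every event lasts *d* days. The share still open at the last contact is then *d*/49:
- *d* = 7: 7/49 = 14%
- *d* = 14: 14/49 = 29%
- *d* = 28: 28/49 = 57%

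The durations and the uniform onset are both assumptions. If events cluster soon after device use begins, the shares are lower. The number of events cannot be derived from the protocol.

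**4. Gap at the start.** Training falls between day -42 and day -7 (week -6 to week -1). The first adverse-event check falls between day -7 and day 0.
- Shortest gap: -7 - (-7) = 0 days
- Longest gap: 0 - (-42) = 42 days

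**5. Timing of training.** Section 6.4 and the Section 7 schedule put training before randomisation for both arms. Section 4.2 (Study Design) describes training as part of starting TAI after allocation to the intervention arm. Both could be true if there are two rounds of training, but the protocol does not say so.

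**The case against.** The case against has real force on several points.

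- **An open event is not lost.** It is recorded at the last visit and counted. Only its later course is missing. A reader might infer that device harm is therefore understated. The documents do not support that, since the count of recorded events is unaffected.
- **Seriousness can usually be judged at one contact.** Death, threat to life and hospital admission can be known that day. The disability criterion is met by significant as well as persistent disability, and Section 10.1.1 calls for medical judgement. It would be wrong to say that seriousness cannot be determined. What cannot be learned is whether an event graded non-serious became serious later.
- **Other papers may cover it.** Sections 9.2 and 10.2 point to a state health directive, event forms and a serious-event form that are not shown. They may contain a rule for open events. If they do, that rule conflicts with the flat sentence in 6.8, which would still need limiting.
- **The sentence may have been meant only for outcome assessments.** That is plausible, but it is not what the text says.
- **Safety is not a listed objective or outcome**, and the primary analysis is untouched. Both are true. They limit how much the point matters but do not remove it.

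On the start of collection, a reader might infer that events before baseline are missed. This does not follow. Nothing excludes a look-back at the two baseline checks, serious events may have the telephone route, and nothing says that training includes a live irrigation. Section 6.4 explains early training as a way to let controls start promptly after the study. Because training there is given to everyone before allocation, events from it would not bias the comparison between arms.

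Section 6.9 adds little. Following open events would not capture harms that first arise after the last visit.

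**Conclusion.** The point holds for the end of the window. As written, Section 6.8 together with the Section 7 schedule leaves any AE, ADE or SAE that is open at the second Week 7 visit without a recorded outcome, and no part of the protocol at hand makes an exception. This rests on the plain reading of 6.8 and on the directive and forms not being visible. The number of events affected is unknown and may be small among 24 participants. The 14%, 29% and 57% illustrate the mechanism and are not estimates.

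For the start of the window, only a narrower statement is supported. No adverse-event check is scheduled for 0 to 42 days after training, the opening of reporting and the look-back are undefined, and the sections on when training occurs need reconciling.

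The change is worth making because it is cheap and improves the safety record. It does not bear on the primary result.

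**What to change.** 1. **Section 6.8.** Limit the sentence to outcome assessments and add an exception, for example: *No outcome assessments will be made after the 6-week assessment. Any AE, ADE or SAE open at the last visit will be followed by telephone until resolved or stable, or for a period fixed here by the sponsor, and its outcome will be recorded.* The length of that period is for the sponsor to choose.
2. **Event forms.** Provide a field for the outcome and its date, if there is none.
3. **Section 7.** State that the first baseline adverse-event check asks about events since consent or TAI training. List events before randomisation apart from the comparison between arms.
4. **Section 4.2 (Study Design), Section 6.4 and Section 7.** Reconcile when training takes place and for whom.

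The cost is a short protocol amendment, one extra question at a visit that already takes place, and a few telephone calls among 24 participants. Data lock may wait a little for the last open events. Sample size and primary analysis do not change.
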